2.2 Rationale for inclusion of subcutaneous interferon gamma

2.2.1 Scientific basis

As our therapy utilizes a transgenic TCR, we are dependent on antigen presentation by the primary tumor through class I MHC. We and others have shown that approximately 80% of MCC tumors downregulate MHC-I presenting an obstacle to T cell efficacy, and this is further true of tumors that have escaped immunotherapy.^{27,62} In 5 patients previously treated in an earlier version of this clinical trial, the only patient with a meaningful clinical response was the single patient with robust baseline class I MHC expression. Furthermore, that patient had loss of class I MHC expression in a single resistant lesion. Despite the small number of patients, this suggests that downregulation of class I MHC may be a key mechanism of resistance to transgenic TCR T cell therapy. However, this class I downregulation is typically reversible with one of several interventions, which include radiation treatment, epigenetic modifiers, chemotherapy, and cytokine treatments.²⁷ Earlier versions of this trial included either single fraction radiation to a subset of lesions (n=3 patients) or chemotherapy treatment (n=2 patients) without clinical efficacy in patients without baseline class I MHC expression. This indicated a different strategy was necessary to efficiently upregulate class I MHC in tumors.

2.2.3 Interferon gamma- safety and clinical results

Interferon gamma is FDA-approved for the treatment of chronic granulomatous disease at a dosage of 50mcg/m² given three times weekly, and is generally tolerated with the known common (>10%) side effects of fever, headache, chills, fatigue, rash, diarrhea, vomiting and injection site reactions. The peak concentration of interferon gamma occurs in 7 hours and is 0.6ng/ml in plasma, with a half-life of 6 hours. Importantly this concentration is associated with significant class I MHC upregulation in Merkel cell carcinoma cells *in vitro* (Figure 10B). Use of subcutaneous interferon gamma in cancer patients has been explored in a previously reported phase 0 trial conducted in sarcoma patients.⁶³ In this trial, administration of interferon gamma was well tolerated and resulted in upregulation of class I MHC in patient tumors and increases in measures of tumor inflammation. Interferon gamma at standard dosing has been given in combination with the PD-1 inhibitor nivolumab in a phase I clinical trial of over 20 patients with no evidence of increased immune related adverse events related to nivolumab (no cases of

grade III or greater immune toxicity during combination treatment) or potentiation of side effects from interferon gamma ([name], personal communication, manuscript in preparation).

2.3 Rationale for administration of TCR-transgenic T cells in the context of treatment with avelumab or Pembrolizumab as a standard of care

2.3.1 Avelumab and Pembrolizumab - Scientific basis

Our data from current T cell therapy trials, protocols 2586 and 9245, strongly support inclusion of avelumab. In protocol 2586, combining autologous *ex vivo* expanded anti-MCPyV T cells with HLA upregulation but without immune checkpoint blockade for MCC, we observed only one patient out of four responding. We further noted that the patient who responded had much lower PD-1 expression on their infused T cells, as compared to patients who did not respond. We thus hypothesized efficacy may be augmented by combination treatment (Figure 5), combining three immunotherapies (“triple therapy”): T cells, class I MHC upregulation, and PD-L1 blockade with avelumab. Indeed, in protocol 9245 combining T-cells with HLA-upregulation and avelumab, we noted improved response rate with 4 of 6 patients responding, including several durable complete responses. We have noted no worsened toxicity with addition of avelumab.

Multiple ICIs have been studied in MCC, including avelumab (anti-PD-L1), pembrolizumab, and nivolumab (anti-PD-1). All are showing clinical effect, and all would be expected to synergize with T cell therapy. Both Avelumab and Pembrolizumab have been FDA approved as standard of care treatments in MCC, and for this reason, they have been chosen as two alternatives for use in this trial.

Table 4: Toxicities of avelumab observed among 88 patients with advanced MCC treated as part of the JAVELIN-200 trial

	Grade 1-2	Grade 3
Fatigue	21 (24%)	0
Infusion-related reaction*	15 (17%)	0
Diarrhoea	8 (9%)	0
Nausea	8 (9%)	0
Asthenia	7 (8%)	0
Rash	6 (7%)	0
Decreased appetite	5 (6%)	0
Maculopapular rash	5 (6%)	0
Blood creatine phosphokinase increase	1 (1%)	1 (1%)
Lymphopenia	0	2 (2%)
Blood cholesterol increase	0	1 (1%)
Aminotransferase increase	0	1 (1%)
Potential immune-mediated treatment-related adverse event†		
Hypothyroidism	3 (3%)	0
Hyperthyroidism	2 (2%)	0
Pneumonitis	1 (1%)	0
Type 1 diabetes mellitus	1 (1%)	0

2.3.2 Avelumab - Clinical experience & safety

Avelumab (trade name Bavencio) is a recently FDA-approved fully humanized monoclonal antibody targeting PD-L1 with indications for Merkel cell carcinoma and advanced bladder cancer.^{7,64} As described above, we believe the addition PD-1 axis blockade to T cell therapy essential due to high PD-1 expression on infused T cells and improved efficacy signal combination therapy. Major side effects include: infusion reactions, immune related adverse events (iRAEs), and other. Infusion reactions are a well-characterized side effect of infusional antibody therapy and occur with 17-22% of patients receiving Bavencio⁷. Consistent with package insert/manufacturer's guidelines, patients will be premedicated with acetaminophen and an H1 blocking antihistamine prior to each infusion, infusions will be given slowly, and patients will be monitored closely for the development of infusion reaction. iRAEs are a well-described complication of any PD-1 axis blocking agent; for avelumab the most commonly reported include pneumonitis, colitis, hepatitis, endocrinopathies, and type 1 diabetes. Thyroid endocrinopathies are the most common iRAE (occurring in up to 6% of patients) and will be closely monitored for with regular blood work according to manufacturer's recommendations.

Pneumonitis is the most severe reported complication. Among all patients receiving avelumab, pneumonitis is reported per FDA labelling insert as occurring in 1.2% (21/1738) of patients receiving avelumab. There has been one reported case (0.1%) of a patient with Grade 5 pneumonitis resulting in death, one (0.1%) with Grade 4, and five (0.3%) with Grade 3 pneumonitis. Immune-mediated pneumonitis led to permanent discontinuation of avelumab in 0.3% (6/1738) of patients. Finally, other side effects include fatigue, arthralgias, and headache (see table 4). Avelumab has been successfully given with ex vivo expanded T cells in 6 MCC patients, with no increased toxicity seen.¹³ As detailed below, avelumab dosing will be given at standard dose level and interval.

Pembrolizumab is a fully humanized anti PD-1 antibody also FDA approved in MCC. It has a similar incidence of immune related adverse events to avelumab in trials of MCC patients and has a lower incidence of infusion reactions than avelumab. It has also been given safely in combination with adoptive transfer of Chimeric antigen receptor modified T cells in several trials⁶⁵⁻⁶⁷, suggesting it is likely to be safe in combination with adoptive T cell transfer in this trial.

2.4 Rationale for inclusion of biopsies

Serial biopsies are very informative for determining whether T cells are preferentially localizing into the tumor environment and interactions between tumor and microenvironment. These can help to guide future studies. If treatment is effective, features of tumor-enriched T cells can be studied to optimize future T cell therapy products, and TIL can be investigated for epitope spreading. If the treatment is ineffective, study of the tumor microenvironment will allow determination of the reason for treatment failure and whether it is a tumor intrinsic or T cell intrinsic defect. We have developed a suite of tools to optimize information from small biopsies (multiplex immunohistochemistry, single cell RNA sequencing) in order to maximize benefit from tiny clinical specimens and reduce risk to research participants (Figure 11 and 12).

Without treatment, metastatic MCC is near uniformly fatal. Spontaneous regressions have been reported in up to 1% of patients, therefore we will conservatively define a comparison response rate as 5% to allow for this and also for the possibility of very delayed checkpoint inhibitor response (although these have not been reported in MCC).^{6,7} There are no FDA-approved or known durably effective treatments for patients with advanced MCC tumors refractory to checkpoint blockade (hence the rationale for pursuing this population). Therefore, success in even a minority of patients would significantly advance the field.

Please see biostatistical section for further details on efficacy assessment and power calculation. In brief, in order to meet this endpoint, at least 3 of 16 patients will need an objective response (best response of partial response or complete response) by RECIST 1.1 criteria.⁷⁰

3.2 Secondary Objectives

3.2.1 Persistence

Persistence of infused transgenic T cells in peripheral blood

3.2.2 Migration

Migration of infused transgenic T cells into tumor tissue

3.2.3 Progression free and overall survival

Determine progression free and overall survival of treated individuals

3.2.4 Determination of preferred dose of FH-MCVA2TCR

Please see section 4.4 for details on dose escalation

3.2.5 Response rate by immune RECIST

Determine objective response rates by immune related RECIST criteria. Please see Hodi *et al* 2018 for definition of iRRC criteria.⁷¹

3.3 Exploratory Objectives

Our study includes a number of exploratory objectives. These include phenotype of infused T cells that persist and localize to tumor, functional capacity of infused transgenic T cells, determination of the presence or absence of epitope spreading (broadening of immune responses) to other MCPyV and/or neoantigen epitopes in the peripheral blood and/or tumor environment, and evaluation of changes in the tumor tissue and microenvironment that may correlate with success and/or failure of the ATTAC regimen. These exploratory objectives are not anticipated to result in direct conclusions but instead develop hypotheses for future trials.

3.4 Projected Target Accrual

Table 5: Targeted / Planned Enrollment			
Ethnic Category	Patient Numbers		
	Females	Males	Total
Hispanic or Latino	0	1	1
Not Hispanic or Latino	6	9	15
Ethnic Category Total of All Patients	6	10	16
Racial Category			
American Indian / Alaska Native	0	0	0
Asian	0	0	0
Native Hawaiian or Other Pacific Islander	0	0	0
Black or African American	0	0	0
White	6	10	16
More than One Race	0	0	0
Racial Categories: Total of All Patients	6	10	16

All racial groups and ethnicities will be included and participation of members of under-represented groups welcomed. **These targeted/planned enrollment numbers are based on relative percentages of race/ethnicity reported for MCC cases in the Surveillance, Epidemiology, and End Results (SEER) cancer registry database.¹** There is a white predominance due to the well described MCC risk factor of UV exposure.⁷²

Sex/Gender

Males	63%
Females	37%

Ethnicity

Hispanic/Latino	5%
Not Hispanic/Latino	95%

Race

American Indian/Alaska Native	<1%
Asian	<1%
Native Hawaiian/Pacific Islander	1%
Black/African American	1%
White	96%

4. STUDY DESIGN AND INVESTIGATIONAL PLAN

4.1 Design: Phase I/II single-arm dose-escalation non-masked interventional study

The study will be a phase I/II, non-masked (not blinded), interventional study aimed at treating up to 16 HLA*A0201 patients with metastatic MCC that has progressed despite immune checkpoint inhibitor therapy (PD-1 or PD-L1 inhibitor). All patients will receive study interventions.

[figure not shown]
Patients may receive the other, standard-of-care portions of the ATTAC regimen in addition to T cells. This includes the PD-L1 inhibitor avelumab. Please see **Section 6/treatment plan** for further details).

Patients will receive up to two T cell infusions. Please see **6.4.4** for details regarding selection of one versus two cycles of T cell therapy.

Any patient experiencing treatment related grade 3 or 4 toxicity (except for the expected toxicity specifically excepted/outlined in **Section 12.6**) will immediately stop receiving T cell infusions, avelumab, and class I HLA upregulation. They will receive treatment as appropriate for their condition (see **Section 7** and **Section 12**). They will continue to be followed for response/outcome. Patients with infusion reactions to avelumab may receive pembrolizumab for first or subsequent infusions.

As a criterion for enrollment into the trial, participants must agree to biopsies of tumor tissue if medically feasible. A minimum of 4 biopsies will be performed as clinical status allows: prior to interferon gamma administration, 1-2 days prior to T cell infusion, 2 weeks after, and 12 weeks after the first full dose T cell infusions. However, should there be no tumor tissue that is accessible for biopsy, patients will still be considered for participation at discretion of the investigator. Similarly, should an investigator or treating physician determine that a biopsy cannot be performed safely for clinical reasons (e.g., no safe approach), biopsies may be cancelled or retimed at the investigator or treating physician's discretion.

4.2 Schematic

4.3 Protocol Enrollment

Enrollment to study commences after eligibility confirmation and just prior to leukapheresis. Enrollment is expected to take approximately 2 years. Study treatment with initial follow-up is expected to be approximately 1 year. All patients who receive treatment with FH-MCVA2TCR should be followed for at least 15 years after the final infusion for safety evaluations in the long-term follow-up (LTFU) portion of the study. The anticipated duration of the study, excluding LTFU assessments, is approximately 3.5 years.

4.4 Staggering and Dose Escalation

At least three patients will be treated on part I. In part I, patients will be treated with a lower-dose first infusion. Each part I patient must complete their dose-limiting-toxicity (DLT) evaluation period (28 days) after their first T cell infusion before the next part I patient may receive their first infusion. This allows for an ample buffer/window to evaluate for potential cytokine release syndrome and/or neurotoxicity, before proceeding to next patient. After three patients have received their first T cell infusion and completed the 28 day DLT evaluation after the lower first dose infusion, with one or fewer patients experiencing grade 3-4 d related adverse events as defined in **Section 12**, the study may move to part II. If two or more of the first three patients have a treatment-related grade 3 or 4 toxicity, or if any of the first three patients experiences a treatment-related death, at that point the trial will be immediately suspended. We will consult with the data and safety monitoring board (DSMB), and a detailed review of the potential causes of toxicity undertaken. We will reconvene with the DSMB and consideration will be given to changing the cell dose or construct if the T cells were implicated. In that scenario, the dose escalation will be restarted and an additional three patients treated before proceeding to the part II portion of the study. Part I will continue until 3 patients are treated at the lower dose level. If the manufacturing process is short of the intended dose targeted for the patient, whatever smaller dose is available from a single manufacturing run will be given.

For the first three patients treated on part II, the staggering interval will continue as for part I, with each treated patient completing their 28-day DLT evaluation period after first T cell infusion before the next part II patient may be treated at that dose. If two or more of the first three part II patients have a treatment-related grade 3 or 4 toxicity, unless a toxicity specifically accepted in **Section 12.5 and 12.6**, or if any of the first three patients experiences a treatment-related death, at that point the trial will be immediately suspended. We will consult with the data and safety monitoring board (DSMB), and a detailed review of the potential causes of toxicity undertaken. We will reconvene with the DSMB and consideration will be given to changing the cell dose to the part I dose level and/or other protocol modifications on guidance of the DSMB. If instead three part II patients have received their first T cell infusion and completed the 28 day DLT evaluation after the lower first dose infusion, with one or fewer patients experiencing grade 3-4 related adverse events as defined in **Section 12**, staggering restrictions will be lifted and there will be no specific staggering requirement.

As patients eligible for second infusion will have tolerated a previous exposure to the same T cell product, between-patient staggering intervals will not apply for second infusion. However, patients will be monitored for a second 28-day DLT period and safety events recorded. Patients previously treated with lower doses of T cells on earlier versions of this trial will be eligible to receive up to an additional 2 doses of TCR transgenic T cells, starting at the dose level for newly entering patients provided that they meet eligibility criteria in **Section 5** before each additional dose.

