2.1.12 FH-MCVA2TCR Dose Rationale

Our prior endogenous cell therapy trials targeted an infused dose of 10 billion (10^{10}) MCPyV-specific endogenous CD8⁺ T cells per square meter, or approximately 20 billion (2×10^{10}) CD8⁺ T cells per infusion. No dose limiting toxicities were observed and the maximum actual infused dose was 26 billion for protocol 2586 (HLA upregulation + T cells) and 17.7 billion for protocol 9245 (HLA upregulation + T cells + avelumab).

For the present study, our goal dose is 1 billion (10^9) MCPyV-specific TCR transgenic CD8⁺ T cells for the initial low dose part I infusion, and 5 billion (5×10^9) MCPyV-specific TCR transgenic CD8⁺ T cells for the second dose infusion or part 2 infusions. CD8⁺ and CD4⁺ cells are co-cultured and transgenic CD4⁺ cells will also be included. The dosing will be based on CD8⁺ T cells for consistency in formulation. Please see **Section 6.4** for additional dosing information. This dose was selected for several reasons: it is achievable in an approximately 2 week production, it is similar to dosing for TCR transgenic T cells for other disease processes, and it is similar to doses given to 3 previous patients on previous versions of this trial with no toxicity attributed to the transferred T cells. All patients included in this study will be adult and are thus expected to have similar body surface areas, and thus we have selected a flat rather than weight-based dosing; this approach is used with dosing with that of other transgenic T cell products for adults including FDA-approved CAR-T therapies (for example, Kymriah).

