6.1 Overall schema

In part I, the first T cell infusion will be up to 1×10^9 tetramer positive CD8+ T cells. Although targeted at 1:1, the actual number of transgenic CD4+ T cells will vary between individuals due to interpersonal

variability (cells are co-cultured). Please see **Section 6.4** for maximum infused transgenic T cells, and **Section 2.1.12** for dose rationale. If patients have progressive disease and tetramer positive T cell persistence below 5% of peripheral CD8+ T cells, a second infusion may be administered at a higher dose of up to 5×10^9 tetramer positive CD8+ T cells. In part II, the initial and potential second T cell dose will be up to 5×10^9 tetramer positive CD8+ T cells.

Transgenic T cells and interferon gamma are investigational, and avelumab or pembrolizumab are provided as standard of care. Therefore, duration of avelumab or pembrolizumab infusions is provided as a suggestion only and may be shortened or extended on the medical judgement of the treating oncologist.

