6.4 FH-MCVA2TCR Infusions

FH-MCVA2TCR will be administered by IV infusion at Fred Hutch (or at University of Washington Medical Center (UWMC) if the patient is hospitalized). T-cell infusions will be given preferably at least

48 hours before the next dose of avelumab or pembrolizumab. However, the infusion may be delayed if required for clinical reasons. Patients will receive either 1 or 2 infusions of FH-MCVA2TCR. Infusions will be ideally scheduled for 12 weeks apart; however, they may be given earlier in the case of early disease progression or later in the event of a need for bridging chemotherapy treatment.

Patients in the part I portion will receive a lower dose for the first infusion of up to 10^9 (one billion) TCR A2-MCC1 transgenic CD8+s, and then up to 5×10^9 (five billion) TCR A2-MCC1 transgenic CD8+ T cells at the second infusion. Patients in the part II portion will receive a full dose of up to 5×10^9 (five billion) TCR A2-MCC1 transgenic CD8+ T cells at both infusions. Infusions will also include CD4+ T cells that will vary naturally between patients as the cells are co-cultured; the total allowable transgenic cell dose (including transgenic CD8+s and CD4+s) will be 10 times higher than the targeted CD8+ dose (e.g., 10^{10} for low dose infusion and 5×10^{10} for standard dose infusion respectively).

Patients previously treated on the protocol at lower cell doses than currently available will be eligible to re-enter the protocol to receive up to 2 additional infusions.

T cells will be infused intravenously through a blood component filter set on an electronic infusion device over approximately 60 minutes. The infusion bag will be gently mixed periodically during the infusion. All patients will be observed for 2 hours post infusion and will be released if no AE requiring prolonged hospitalization have occurred.

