6.4.1 Preparation of Cell Product

All manufacturing activities are conducted using approved written procedures performed by trained, qualified personnel in accordance with current Good Manufacturing Practices (cGMP) and current Good Tissue Practices (cGTP) guidelines. Quality assurance oversight and review is provided to assure regulatory compliance and safety of therapeutic products. It is anticipated to take approximately 9-14 days to manufacture a product in most cases.

If a product cannot be formulated to meet a target cell dose, the cell product should be infused at or as close as possible to the total transgenic CD8+ T-cell dose. A product will be considered evaluable for response if it contains $\geq 10\%$ of the scheduled CD8+ transgenic T cell dose; however, lower dosages of cells may be administered at the discretion of the investigator.

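### The part II rule that lifts staggering sets no minimum infused dose, so a part II patient given no more than the part I CD8+ dose counts toward clearing the higher dose

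*Combined protocol and SAP*

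**What the plan says.** Section 4.4 staggers the first three part II patients: each completes a 28-day DLT period after the first infusion before the next is treated. Two or more of the three with related grade 3-4 toxicity, or any treatment-related death, suspends the trial. Otherwise the stagger is lifted when "three part II patients have received their first T cell infusion and completed the 28 day DLT evaluation after the lower first dose infusion", provided that no more than one of them had such toxicity.

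The dose provisions around this rule are:

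- **Section 6.1.** "In part II, the initial and potential second T cell dose will be up to" 5×10^9 tetramer-positive CD8+ cells. The part I first dose is likewise a ceiling, of 1×10^9.
- **Section 4.4, on a manufacturing shortfall.** "whatever smaller dose is available from a single manufacturing run will be given".
- **Section 6.4.1.** "A product will be considered evaluable for response if it contains" at least 10% of the scheduled CD8+ dose, but "lower dosages of cells may be administered at the discretion of the investigator".
- **Section 6.2.** A second collection after an insufficient product is permitted, not required.
- **Section 6.4.** CD4+ cells vary between patients, and "the total allowable transgenic cell dose (including transgenic CD8+s and CD4+s) will be 10 times higher" than the targeted CD8+ dose. This is a separate cap and also sets no minimum.

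**The concern.** The stagger exists so that cytokine release syndrome and neurotoxicity can be seen in one patient before the next is exposed. In part II the new exposure is the five-fold higher CD8+ dose. The lifting rule counts patients by the part they belong to, not by what was infused. The only dose words in the lifting sentence describe the part I regimen.

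A part II patient whose product falls to the part I level or below tells the team little about the higher CD8+ dose, yet that patient's 28 uneventful days help to clear it. The wait could then end with fewer than three first infusions observed above the part I CD8+ level. Up to 13 patients enter part II (Section 13.2.2), so up to 10 could follow the gate without a required interval.

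The protocol recognises that a short product affects interpretation of response and sets a floor for that purpose. It sets none for this safety gate.

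**Working it through.** **Dose arithmetic.** The Background states a five-fold reduction for the part I first dose: 5×10^9 / 1×10^9 = 5, which agrees. The part I level is therefore 1/5 = 20% of the part II ceiling. The response-evaluability floor is 0.10 × 5×10^9 = 5×10^8, half the part I dose, so borrowing it for safety would not close the gap.

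**Toxicity rates.** Section 13.2.2 evaluates its stopping boundary at true rates of 20% and 60%. An exact recursion over that boundary gives suspension probabilities of 0.062 and 0.847, against the stated 0.06 and 0.84 from 5,000 simulations, so these figures reproduce. Assigning 60% (or 40%, the protocol's acceptability limit) to full dose and 20% to short dose is an assumption made here.

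**Effect by number of short patients.** The gate passes with at most one toxicity in three. At 60% full and 20% short, the probability of passing is 0.352, 0.544, 0.768 and 0.896 with 0, 1, 2 and 3 short patients. For one short patient:

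- no toxicity: 0.4 × 0.4 × 0.8 = 0.128
- exactly one: 2 × 0.6 × 0.4 × 0.8 + 0.4 × 0.4 × 0.2 = 0.416
- sum: 0.544

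**Effect averaged over a shortfall rate.** Let s be the share of products at or below 20% of target. The documents do not give it; 5%, 10% and 20% are assumed.

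- Chance that at least one of three is short: 1 − (1 − s)^3 = 14%, 27%, 49%.
- Rule as written: p = p_full(1 − s) + p_short·s, and P(pass) = (1 − p)^3 + 3p(1 − p)^2.
- Rule proposed below: let q be the number of qualifying patients and t all toxicities, with f = 0 at t = 2 and f = 1 at q = 3. Then f(q,t) = [s·p_short·f(q,t+1) + (1 − s)(p_full·f(q+1,t+1) + (1 − p_full)·f(q+1,t))] / [1 − s(1 − p_short)].

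Example at s = 0.20 with 60%/20%. As written, p = 0.48 + 0.04 = 0.52 and P(pass) = 0.48^3 + 3 × 0.52 × 0.48^2 = 0.470. Under the proposal the denominator is 0.84, with f(2,1) = 0.381, f(2,0) = 0.971, f(1,1) = 0.145, f(1,0) = 0.594, f(0,1) = 0.055 and f(0,0) = 0.312.

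| Toxicity full / short | Rule | s = 0 | s = 5% | s = 10% | s = 20% |
|---|---|---|---|---|---|
| 60% / 20% | as written | 0.352 | 0.381 | 0.410 | 0.470 |
| 60% / 20% | proposed | 0.352 | 0.343 | 0.333 | 0.312 |
| 40% / 20% | as written | 0.648 | 0.662 | 0.676 | 0.704 |
| 40% / 20% | proposed | 0.648 | 0.634 | 0.620 | 0.586 |
| 20% / 20% | as written | 0.896 | 0.896 | 0.896 | 0.896 |
| 20% / 20% | proposed | 0.896 | 0.884 | 0.870 | 0.837 |

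Against s = 0, the rule as written gains 2.9, 5.8 and 11.8 points at 60%/20%, and 1.4, 2.8 and 5.6 points at 40%/20%.

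**Delay from the proposal.** Expected extra staggered patients, ignoring suspension, are 3s/(1 − s) = 0.16, 0.33 and 0.75. At 28 days each this is about 4, 9 and 21 days. Accrual of 8 per year (Section 13.1) averages 365/8 ≈ 46 days between patients.

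**The case against.** The stagger sentence in the same paragraph of Section 4.4 speaks of the next part II patient being treated at that same dose, which ties the wait to the part II dose. This shows what was intended. It sets no floor, however, and the lifting sentence does not repeat it.

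Short products may also be rare. Section 2.1.12 says of the chosen dose that "it is achievable in an approximately 2 week production", and Section 2.1.4 expects targets to be easier to reach than with endogenous cells. A reader might infer from the 0.25-14% of target quoted in Section 2.1.4 that shortfalls will be common. The documents do not support that: those figures describe the earlier endogenous products, and avoiding such shortfalls is one reason given for the transgenic approach.

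Other evidence on dose exists. Part I second infusions may reach 5×10^9, with a second 28-day DLT period recorded. These are conditional, unstaggered and outside the gate. Section 2.1.12 calls the dose "similar to doses given to 3 previous patients on previous versions of this trial", with no toxicity attributed to the cells, but gives no dose level; Section 2.2.1 describes radiation or chemotherapy, not interferon gamma, for class I upregulation in those versions. Endogenous products reached 26 and 17.7 billion cells without dose-limiting toxicity, but are a different product.

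Passing the gate ends only the between-patient wait. The Section 13.2.2 boundaries, individual discontinuation, monthly review and ad hoc DSMB meetings continue. At 46 days between patients on average, a 28-day wait would often not bind. These points limit the size of the concern. None requires exposure above part I before the wait is lifted.

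**Conclusion.** The gap is real on the text. The lifting rule names an infusion that part II patients do not receive, sets no minimum dose, and lets a patient at or below the part I CD8+ level count toward clearing 5×10^9. The comparison is of CD8+ cells, the basis for dosing; total transgenic exposure may still differ through CD4+ cells.

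The effect is modest: a rise in the chance of passing of about 3 to 12 points at 60%/20%, or about 1 to 6 points at 40%/20%. Both ranges rest wholly on assumed shortfall rates of 5-20% and an assumed link between dose and toxicity. The true shortfall rate is unknown.

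A reader might infer that the higher dose will go unobserved, or that safety monitoring fails once the stagger is lifted. The documents support neither. Short products are a contingency, and the overall stopping boundaries and DSMB review stay in force. The figures describe passage of one gate, not patients harmed or the overall probability of suspension. The correction should be made because the rule, followed as written, can defeat its own purpose and is cheap to repair.

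**What to change.** In Section 4.4, part II rule:

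- Delete the reference to a lower first dose infusion.
- Count toward the three only part II patients whose first infusion exceeded 1×10^9 transgenic CD8+ cells. State that this ensures exposure above part I, not full dose; a patient just over the threshold would still qualify.
- Still infuse short products, keep those patients in all safety monitoring, and count their toxicities toward suspension (two related grade 3-4 toxicities before three qualifying patients complete 28 days). Keep the suspension for treatment-related death.
- Tabulate toxicity by infused CD8+ dose, with total transgenic dose alongside, as well as by part.

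This needs protocol wording and one table, using cell counts that dosing already requires. It adds one 28-day interval per short product among the early part II patients, about 4 to 21 days in expectation under the assumed rates. Because short-dose toxicities count while those patients do not, the gate becomes slightly stricter. In a safe regimen (20% toxicity at both doses) passing falls from 90% to 84-88%; at 40%/20% with 20% short products it falls to 59%, against 65% with none short.
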